5.2.6 Tumour markers

Selected tumour markers will be recorded at baseline and visit 8, and again at visit 5 of repeated courses. These parameters are outlined in Section 5.2.5 of the CTP. However, specific attention will be paid to the markers CA-125, CA 19-9 etc. These will be presented in listings.

5.3 OTHER ENDPOINTS

5.3.1 Demographics

Only derived endpoints are defined here. Standard demographic and baseline characteristics (sex, age, race, etc.) are used as recorded in the eCRF.

Body Mass Index (BMI)

$$BMI \left[\frac{kg}{m^2} \right] = \frac{weight \left[kg \right]}{(height \left[m \right])^2}$$

Time from first histological diagnosis [years] is the time between the date of first histological diagnosis and the date of informed consent:

Time [years] = (informed consent - date of first histological diagnosis + 1)[days] / 365.25

Age at the first Histological diagnosis [years]:

Age [years] = INT(date of first histological diagnosis – birthday)[days] / 365.25,

where the INT function truncates the decimal portion of the value of the argument.

[REDACTED]

[REDACTED]

5.3.3 Extent of exposure

Number of days of administration [N]: Cumulative number of days with an administration of treatment.

Number of courses initiated [N]: course initiated means that the patients received at least one administration of BI 6727 in the initiated course.

Number of courses completed [N]: A course is considered completed if one of the following is true:

- Another course was initiated.
- The patient was observed in the trial until at least 21 days after the last administration of trial medication of the respective course or stopped the trial due to DLT or PD.

Total observation time [in days] = (Date of last observation from the eCRF – first administration of trial medication date in course 1 + 1).

Cumulative total dose [mg] = Sum of doses (administered dose of BI 6727) calculated across all courses.

Total exposure time to the trial drug [days] = duration of “on treatment period” = MINIMUM (date of last trial drug administration of the last course + 21 days, death if occurring earlier than 21 days after the last administration) – date of first administration in the first course + 1 day.

[REDACTED]

[REDACTED]

[REDACTED]

[REDACTED]

[REDACTED]

[REDACTED]

[REDACTED]

[REDACTED]

5.3.5 ECG

- QTcF changes from baseline at each point in time: the QTcF post baseline measurement obtained at time t minus baseline QTcF measurement at time t.

The above endpoint will also be computed for the uncorrected QT interval and for the heart rate (HR). The heart rate (HR) will be derived from RR intervals.

- New*) onset of QT/QTcF > 500 ms (notable prolongation)
- New*) onset of QTcF > 470 ms
- New*) onset of QTcF > 450 ms

*): “New” means not present at any time pre-dose

- Categories of the QTcF increase from baseline to the maximum value: intervals for a given patient as $QTcF \leq 30$ ms, $30 \text{ ms} < QTcF \leq 60$ ms, $QTcF > 60$ ms, (the latter increase reflects a notable change)
- Categories of the QT increase from baseline to the maximum value: intervals for a given patient as $QT > 60$ ms (the latter increase reflects a notable change)
- PR and QRS changes from baseline at each point in time
- PR, QRS and HR percentage changes from baseline at each point in time

5.3.5.1 ECG - Assessment for patients of the extension cohort for additional QT/QTc analysis

Three consecutive ECGs were recorded

at screening, and

- prior to the start of the infusion (baseline)
- 5 minutes before the end of the infusion,
(i.e. around 1 hour, if infusion duration is 1 hour or around 2 hours, if infusion duration is 2 hours, respectively)
- 1 hour after the end of the infusion,
(i.e. around 2 hour, if infusion duration is 1 hour or around 3 hours, if infusion duration is 2 hours, respectively)
- 4 hours
- 24 hours

after the end of infusion of Courses 1 and 2

5.3.5.2 ECG - All other patients

Resting ECG was recorded prior to the start of the infusion (baseline) of treatment courses 1 and 3, directly after the end of the infusion, and again at the end of the treatment course. A series of three consecutive ECGs using dedicated equipment were recorded.

6. GENERAL ANALYSIS DEFINITIONS

6.1 TREATMENTS

6.1.1 Treatment regimens / study intervals

The treatment regimens/study phases with short label, sort order and start date/time included in the treatment set-up in O*C (actual treatment set-up) [REDACTED]

6.1.2 Randomised treatment

Codes, decodes and sort order for initial treatment labels [REDACTED]

6.1.3 Specification of treatments for analyses

“Analysing treatment” will be used for reporting of treatment emergent AEs and to differentiate between screening, on-treatment and post-study safety data. The inequalities start date (in Table 6.1.3: 1 below) \leq onset date of AE $<$ end date will determine whether the AE will be assigned to the “analysing treatment” or not.

The labels of the analysing treatment, analysing numbers (analno), the labels used for displays in the tables as well as start date and end date to be used for reporting of AEs and laboratory values in the CTR, are seen in the table below.

Table 6.1.3: 1 Definition of the label of the analysing treatment, analysis numbers, the labels using for displaying in the tables, start date and end date

Label of the analysing treatment (ANALLBL)	Analysis number (ANALNO)	Label for the columns displayed in the tables	Start date	End date
Screening	5		Date of informed consent If date of informed consent = date of administration then the start date for "Screening"- period will be derived as date of informed consent – 1 day	Start date of treatment course 1

Table 6.1.3: 1 Definition of the label of the analysing treatment, analysis numbers, the labels using for displaying in the tables, start date and end date - continued

Label of the analysing treatment (ANALLBL)	Analysis number (ANALNO)	Label for the columns displayed in the tables	Start date	End date
Treatment course 1 analysis	4	- use treatment specification of the initial treatment [REDACTED] and column 'NAME in E_TPATT'	Date of first administration of BI 6727 within the treatment course 1	Date of first administration of BI 6727 within the treatment course 2, Or, Start date of actual treatment post-study.
Treatment course 1 analysis	4	Total	Date of first administration of BI 6727 within the treatment course 1	Date of first administration of BI 6727 within the treatment course 2, Or, Start date of actual treatment post-study.
All course analysis	3	- use the treatment specification of the initial treatment [REDACTED] and column 'NAME in E_TPATT'	Date of first administration of BI 6727 within treatment course 1	Start date of post-study interval [REDACTED]
All course analysis	3	Total	Date of first administration of BI 6727 within the treatment course 1	Start date of post-study interval [REDACTED]

Table 6.1.3: 1 Definition of the label of the analysing treatment, analysis numbers, the labels using for displaying in the tables, start date and end date - continued

Label of the analysing treatment (ANALLBL)	Analysis number (ANALNO)	Label for the columns displayed in the tables	Start date	End date
Post-study	6	- use the treatment specification of the initial treatment [REDACTED] and column 'NAME in E_TPATT'	Start day of post-study-interval	Date of Data Base lock+1day

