#### **4.1.6 Selection and timing of doses for each subject**

BI 6727 will be administered as a short infusion over 60 minutes using an infusion pump, on day 1 of each course (the start and end time of the infusion needs to be documented in the e-CRF). Immediately following the infusion of BI 6727 the infusion tubing will be washed with 100 mL physiological sodium chloride (0.9% NaCl) solution for a maximum duration of 10 minutes (The end time of the washing step needs to be documented in the e-CRF). BI 6727 should be administered strictly intravenously.

Initially, three patients will be treated per dose level. When at the ongoing dose level one patient experiences drug-related dose limiting toxicity (DLT; for definition, please refer to section 5.2.1) the number of patients treated at that dose level will be increased to a maximum of six evaluable patients. When no further patient experiences DLT the dose will be escalated to the next level. When two or more patients experience DLT in any dose cohort, other than the

expansion cohort at MTD level, enrolment into this dose cohort will be stopped. In order to define the maximum tolerated dose (MTD) three additional patients will be treated at one dose tier below unless six have already been treated at that dose tier. The MTD (see also section 5.2.1) is the highest dose at which not more than one patient out of six experiences DLT (R01-0028). Should safety data of patients treated at the next lower dose indicate a sufficient safety margin another escalation to an intermediate dose can be chosen after discussion between the investigator and the clinical monitor.

Once the MTD is determined patient enrolment at higher dose tiers will be suspended. Further patients will be included at the MTD level until a total of 24 patients will have been treated at the MTD.

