#### Visit 8 - day 22 ( $\pm 2$ )

Visit 8 is the last visit of the initial treatment course. This visit may coincide with day 1 of the following treatment course. Examinations which are due on both present visit and the day of BI 6727 administration need to be documented only once (in the day 22 visit).

- vital signs (blood pressure, pulse rate)
- ECOG performance score
- adverse events
- changes in concomitant therapy
- safety lab including haematology, biochemistry, coagulation parameters
- Endosonography or sonography (optional)
- resting ECG (series of three consecutive ECGs using dedicated equipment)

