Note: For calculating the change in CTCAE grade from baseline/ pre-dose level, patients with a CTCAE grade of -9 will be reviewed on a case-by-case basis. If there is no suggestion that the corresponding laboratory value is of clinical significance, these values will be changed to -7 and treated as a CTCAE grade of 0 for analyses. All other values with CTCAE grade -9 will be regarded as CTCAE grade -8. Values with a CTCAE grade of -8 will either be removed from analyses concerning determination of baseline and worst CTCAE grade or if needed the category “not covered by CTC criteria” will be included. Values with CTCAE grades of -7 and -8 will be displayed in two separate listings.

In a similar manner, patients with a CTCAE grade of -1 will be reviewed on a case-by-case basis. For uric acid, values with CTCAE grade -1 will be regarded as either CTCAE grade 3 or CTCAE grade 1, depending on whether accompanied with physiological consequences or not.

The worst post baseline laboratory value and its CTCAE grade over all treatment courses will be calculated for each laboratory parameter specified above.

The time to worst CTCAE value [in days] will be defined as the time from first administration of trial medication to the first occurrence of the worst CTCAE grade. (Date of first occurrence of worst CTCAE grade – date of first administration of trial medication + 1).

The last value on treatment will be determined using a similar algorithm to the adverse events, and presented descriptively.

The change of the CTCAE grade of the lab value will be calculated

- from baseline to the last laboratory value on treatment
- from baseline to the worst value on treatment

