7.7.2 Laboratory data

The analyses of laboratory data will be descriptive in nature and will follow the standard procedure laid down in the [DM & SM](#) (Guideline 'Display and Analysis of Laboratory Data').

Patients will be counted under the initial treatment. Separate listings for patients treated under different doses will be created. The analysis of laboratory data will use the same ‘analysing treatments’ as described for the AEs.

Single time courses by initial treatment will be used to display laboratory values over time. The graphs may be truncated if sufficient data is not available. These graphs will be displayed in Chapter 16.1.9.2 for the following parameters, using the BI normalised values for Haematology and Differentials, and the multiples of the ULN for Substrates and Enzymes:

Haematology: Haemoglobin, WBC count and Platelets

Differentials: Neutrophils (absolute count)

Substrate: Creatinine, Total Bilirubin and Creatinine Phosphokinase

Enzymes: AST, ALT and γ -Glutamyl transpeptidase (GGT)

In addition, laboratory tests will be analysed within the treatment courses as defined below. Maximum CTCAE grades will be tabulated by treatment course and over the entire trial.

Where applicable, standard CTCAE grading Shift tables from first visit to end of trial will be generated in Appendix 16.1.9.2.

Number of patients treated [N (%)]

Number of patients with maximum change of CTCAE grade [N (%)]

Number of patients with transition of CTCAE grade:

- from baseline to the last value on treatment [N (%)]
- from baseline to the worst grade on treatment [N (%)]
- from worst to the last value on treatment [N (%)]

Clinically relevant abnormalities [REDACTED] will also be summarised.

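### In the visible SAP text, a laboratory sample taken before the infusion on a redosing day falls outside the course 1 analysis period, although the protocol records it under visit 8 of course 1

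*SAP*

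**What the plan says.** SAP 6.1.3 places an adverse event in a period when the start date is no later than the onset date and the onset date is strictly earlier than the end date: "onset date of AE $<$ end date will determine whether the AE will be assigned to the" period concerned. The same section extends the boundaries to laboratory data, giving the labels "as well as start date and end date to be used for reporting of AEs and laboratory values in the CTR", and SAP 7.7.2 repeats that laboratory data use the same periods as adverse events. In Table 6.1.3: 1 the course 1 analysis ends at: "Date of first administration of BI 6727 within the treatment course 2, Or, Start date of actual treatment post-study".

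Protocol 6.2.2.1 says of visit 8, due on day 22 (±2): "This visit may coincide with day 1 of the following treatment course". Examinations due at both visits are documented once, in the day 22 visit. Protocol 6.2.2.2 also lets laboratory results from the last visit of the preceding course serve for day 1 of a repeat course.

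Two laboratory outputs could depend on the boundary. SAP 7.7.2 states: "Maximum CTCAE grades will be tabulated by treatment course and over the entire trial". It also lists transitions from worst to last value on treatment, and SAP 5.2.5 says: "The last value on treatment will be determined using a similar algorithm to the adverse events".

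**The concern.** The protocol foresees a single sample that closes course 1 and clears the patient for course 2. By visit it is the day 22 value of course 1. By the SAP's dates it is not in the course 1 period at all. The SAP therefore gives two answers for the same record. SAP 5.2.5 lists day 22 in the first-course schedule and calculates change from baseline at the last visit of each course, and SAP 6.7 labels visits by the protocol flow chart. SAP 6.1.3 excludes the record.

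The day 22 blood count matters because protocol 7.3.3 makes the first course a separate reporting segment and asks for the time course and reversibility of changes. Protocol 1.4 describes quickly reversible neutropenia as the dose-limiting toxicity of the related compound. In an output built strictly on the course 1 period, a patient who recovers and is redosed on the visit 8 date would lose the value showing recovery. An unresolved grade present before the infusion could be counted in the next course.

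**Working it through.** The plan gives no figure on this point, so the check applies the SAP's rule to the protocol's schedule.

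**Inputs**
- Rule (SAP 6.1.3): a record is in the period if start ≤ date < end.
- Course 1 start: day 1. Course 1 end: D, the date of the course 2 infusion.
- Course 1 laboratory schedule (SAP 5.2.5): days 0–3, 5, 8, 15 and 22. The post-dose days are 2, 3, 5, 8, 15 and 22, which is six.
- Redosing (protocol 3.3.3): not before 22 (±2) days after the start of the previous course. Visit 8 is on day 22 (±2), that is, days 20 to 24.

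**Step 1: visit 8 on the redosing date.** The sample date equals D. The test D < D is false, so the sample is outside course 1. This holds on any of days 20 to 24. If redosing is at least one day after visit 8, the sample date is below D and the sample stays in course 1.

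**Step 2: what remains.** With D = day 22, days 2, 3, 5, 8 and 15 satisfy the rule and day 22 does not. Course 1 keeps 5 of 6 scheduled post-dose laboratory days, and the last is day 15 (±1). Assignment by date and time, or by visit label, would keep 6 of 6.

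**Step 3: elapsed time.** Day 22 − day 1 = 21 days. The excluded date is still inside the 21 days after dosing that protocol 5.2.2 treats as on treatment for adverse events.

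**Step 4: where the record goes.** Table 6.1.3: 1 has rows for screening, course 1, all courses and post-study. There is no course 2 row. The record leaves the course 1 analysis and stays in the all-course analysis. A course 2 destination arises only in a by-course tabulation, such as maximum grade.

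**Step 5: effect by output**
- Visit-based change from baseline (SAP 5.2.5 and 6.7): day 22 is kept, so there is no effect.
- Laboratory graphs over time by initial treatment (SAP 7.7.2): the recovery remains visible.
- Maximum grade, course 1: the maximum over five days differs from that over six only if day 22 held the worst grade. Dropping a recovered value changes nothing.
- Maximum grade, next course: an unresolved pre-infusion grade can be counted there.
- Worst-to-last transition, if run within course 1: the last value becomes day 15. As an illustration, grade 4 on day 15 and grade 0 on day 22 would appear as worst 4, last 4 instead of 4 to 0.
- Adverse events: only those with onset on the redosing date move. Earlier onsets stay in course 1.

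**The case against.** The strongest reply is that little depends on this boundary. SAP 5.2.5 defines the worst value over all treatment courses and the last value on treatment. On that reading a redosed patient's last value comes from a later course, and day 15 never becomes the last value. SAP 7.7.2 does speak of analysing laboratory tests within treatment courses, but a worst-to-last table for course 1 alone is an inference. Carry-over into the next course is also limited, because protocol 3.3.3 requires recovery from clinically relevant drug-related events before retreatment. This stands, and it is why the transition effect is stated conditionally. The by-course maximum grade is explicitly planned, so the boundary still needs a rule.

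The second reply is redaction. SAP 6.1.1 mentions a start date/time in the treatment set-up before its text is blacked out, and SAP 6.7 has a partly redacted same-date rule for laboratory baseline. A hidden time rule cannot be excluded. Against that, the visible table defines its boundaries as dates. It handles one same-date collision, consent on the day of administration, by moving the screening start back one day. It shows nothing comparable at the second infusion, and the visible part of the SAP 6.7 rule concerns only the first dose.

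A reader might infer several stronger things that the documents do not support:
- That first-course tables in general lose the recovery values. Visit-based summaries and the time-course graphs keep them.
- That adverse events need clock times too. The source-document list in protocol 8.2.4 names only the onset date, so a time rule for events would add little.
- That the MTD count is distorted. A DLT with onset before the redosing date stays in course 1, and only one starting on that date could move.
- That the MTD count is safe because a patient with a DLT would never be redosed that day. Protocol 3.3.3 does not say so; it ties retreatment to recovery and to the minimum interval.

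**Conclusion.** The concern holds as a boundary ambiguity in laboratory reporting. Read as printed, SAP 6.1.3 and 7.7.2 put a pre-infusion redosing-day sample outside the course 1 period, while protocol 6.2.2.1 and the visit-based text of SAP 5.2.5 and 6.7 treat it as day 22 of course 1.

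For each patient redosed on the visit 8 date, one of six scheduled post-dose laboratory days leaves the course 1 period, and the last scheduled value moves from day 22 (±2) to day 15 (±1). The documents do not say how many patients this concerns, so no trial-level size can be given. The consequence is confined to period-based outputs: maximum CTCAE grade by course, and worst-to-last transitions if they are run within course 1.

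The conclusion assumes that the table's dates are applied literally and that no redacted rule overrides them, so confidence is moderate. All analyses are descriptive and no inference is affected. The correction is still worth making, because it is cheap and removes a contradiction in first-course safety reporting.

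**What to change.** Add a footnote to Table 6.1.3: 1. Laboratory samples taken before the infusion on a redosing day belong to the course just completed. If the clock time is missing, samples recorded under visit 8, or under visit 5 of a repeat course, also belong to the course just completed. Align SAP 5.2.5 and 6.7 with this and refer to protocol 6.2.2.1. State in SAP 7.7.2 whether worst-to-last transitions are run within course 1 or over all courses. Leave the date-based adverse event rule as it is. If a redacted passage already contains such a rule, a cross-reference from the table is enough.

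The cost is minor programming. Infusion times are already collected, since protocol 4.1.6 requires that "the start and end time of the infusion needs to be documented in the e-CRF". SAP 6.7 already contemplates laboratory times, and the visit label covers samples without one.

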6.2 IMPORTANT PROTOCOL VIOLATIONS

Due to the fact that this is a phase I study, no per protocol population is needed, however important protocol violations (PV) should be identified for patients in the treated set (see [Section 6.3](#)). Any PV which may affect safety, efficacy or the patient's rights will be determined.

PVs are summarised into categories and are coded in O*C. [REDACTED]

[REDACTED]

[REDACTED]

Table 6.2: 1 Listing of protocol violations

Category/Code	Description		Comment/Example	Efficacy (E), Safety (S) or Right (R)
A	Inclusion/Exclusion Criteria			
	A1 Criteria related to safety			
	A1.1	Patient has condition that may cause additional risk from study medication	IN 2, 5 EX 1, 3-5, 11, 13	S

Table 6.2: 1 Listing of protocol violations – continued

Category/ Code	Description	Comment/Example	Efficacy (E), Safety (S) or Right (R)
A1.2	Patient has laboratory assessments that may cause additional risk	EX 6-10	S
A1.3	Patient is unable to comply with the protocol	EX 15	S
A2	Criteria related to efficacy		
A2.1	Patient does not have trial diagnosis	IN 1	E
A2.2	Patient does not have ECOG score ≤ 2	IN 4	
A2.3	Chemo-, radio-, or immunotherapy within the past four weeks before start of therapy or concomitant with this trial. This does not apply to steroids and bisphosphonates.	EX 14	E
A2.4	Patient does not have any measurable tumour deposits (RECIST), only for additional patients recruited at the MTD.	IN 6	E
A3	Any other criteria not met that are considered relevant at DQRM/BPRM	n.a.	E/S
B	Legal criteria		
B1	Informed consent not given	IN 3	R
B2	Informed consent after visit 1		R
B3	Patient < 18 years old	IN 2	R
B4	Men or women who are sexually active and unwilling to use a method of contraception, women who are pregnant or breastfeeding	EX 2, 12	R
C	Administration of trial medication not in accordance with the protocol		
C1	BI 6727 taken before PK sampling at visit 2 (treatment course1)	As entered in e-CRF. Create listing, decision at DQRM/BPRM.	E
C2	Criteria for repeated treatment eligibility		
C2.1	Patient continuing on study medication despite experiencing progressive disease and/or clinical progression.	Create listing, decision at DQRM/BPRM.	S

Table 6.2: 1 Listing of protocol violations – continued

Category/ Code	Description	Comment/Example	Efficacy (E), Safety (S) or Right (R)
C2.2	Patient continuing on study medication after experiencing drug-related clinically relevant AE and/or DLT without following recovery.	Create listing, decision at DQRM/BPRM.	S
C2.3	Patient continuing on study medication after delaying a treatment course for more than 6 weeks.	Create listing, decision at DQRM/BPRM.	S
D	Concomitant medication		
D1	Any other chemotherapy, immunotherapy or radiotherapy during the trial	Create listing, decision at DQRM/BRPM.	S, E
E	Missing data		
E1	Missing PK and administration data		
E1.1	Missing PK sampling date and/or time	Create listing, decision at DQRM/BRPM.	E
E1.2	Missing BI 6727 administration date and/or time	Create listing, decision at DQRM/BRPM.	E
E2	Missing response data		
E2.1	Baseline scan of tumour measurement not within four weeks prior to treatment.	Create listing, decision at DQRM/BRPM.	E
E2.2	Different imaging techniques were used for lesion measurement(s) during trial.	Create listing, decision at DQRM/BRPM.	E
E2.3	Missing image(s) at one or more time points.	Create listing, decision at DQRM/BRPM.	E

